6.5 Withdrawal Visit

- Record date and reason for withdrawal.
- If withdrawal occurs during an in-office visit, and if the consent was not withdrawn, obtain the applicable study data using the visit specific data collection forms/steps listed in the sections above.

7 STUDY PROCEDURES/EVALUATIONS

7.1 Study Procedures/Evaluations

Practitioner:

Prior to enrolling patients, the practitioner will complete a Practitioner Characteristics Form which will ascertain types and frequency of typical treatments and retention techniques used to treat adult patients presenting with an AOB.

Patient:

Enrollment. For each patient enrolled, the practitioner will complete an Enrollment Visit Form based upon clinical examination and review of records recording: 1) patients' reasons for seeking treatment; 2) pre-treatment diagnoses (dentofacial characteristics); 3) goals of treatment (practitioner perspective); and 4) treatment plan options, including adjunctive treatment, and treatment plan chosen.

De-identified initial cephalometric x-ray and intra-oral frontal photographs taken prior to treatment initiation will be uploaded for measures of dentofacial characteristics, such as overbite, mandibular plane angle, and incisor angulation (as described above in outcome measures).

At enrollment, after consent, the patient will complete a Patient Enrollment Visit form, which elicits 1) age (from year of birth and date), race/ethnicity, sex, insurance, education; 2) reasons for seeking treatment; 3) treatment recommended as ideal (patient perspective); 4) whether or not accepted ideal recommendation, and if not, why not; and 5) previous orthodontic treatment, if any.

End of active treatment. The practitioner will complete an End of Active Treatment Form based upon clinical examination and review of treatment records recording: 1) any changes in originally accepted treatment plan; 2) treatment result and expected stability outcome; 3) any residual oral habits; 4) patient compliance and adjunctive treatments; 5) current molar relationship; and 6) retention techniques recommended.

De-identified end of active treatment cephalometric x-ray and intra-oral frontal photograph taken in maximum intercuspation will be uploaded for measures of overbite. Practitioner will also obtain an additional intra-oral frontal photograph taken with the incisors slightly apart and upload the de-identified photo for measures of overbite. The practitioner will also measure the height of the right maxillary central incisor using the provided metal ruler.

Patients will complete an End of Active Treatment Form eliciting whether or not AOB was closed, if they were satisfied overall, satisfied with esthetics, satisfied with function, and if they would recommend the treatment they received to a friend if they had similar problem.

Routine visits within the year following end of active treatment. Practitioner will complete a Retainer Use Form based upon clinical history and examination, recording: 1) AOB status and any changes in alignment of upper or lower incisors; 3) assessment of patient's compliance; 4) any retainers and/or regimen changes; and 5) whether any additional adjunctive treatments have been completed since retention began.

Patients will complete a brief Retainer Use Form eliciting whether or not AOB is closed, how much they are wearing upper/lower retainers, and whether or not they are wearing retainers as requested.

Final visit, one year after end of active treatment. Practitioner will complete a Final Visit Form based upon clinical history and examination, recording the same information as on retainer use form and the current molar relationships.

Final intra-oral frontal photographs, one taken in maximum intercuspation, and another one taken with the incisors slightly apart, will be de-identified and uploaded for measurement of overbite. The practitioner will also measure the height of the right maxillary central incisor using the provided metal ruler.

Patients will complete a brief Final Visit Form eliciting whether or not AOB is (still) closed, current usage, if satisfied with retainer experience, satisfied with esthetics, satisfied with function, if they would recommend the treatment received to a friend if they had similar problem, and if satisfied with type of retainers received after treatment.

7.2 Questionnaire Administration

Patient satisfaction will be assessed using a five-point Likert-like scale (very satisfied, somewhat satisfied, neither satisfied nor dissatisfied, somewhat dissatisfied, very dissatisfied), followed by open-ended responses for somewhat/very dissatisfied responses. Whether or not treatment would be recommended to a friend will also be assessed using a five-point Likert-like scale. Patient's compliance with retainer regimens will be ascertained from the perspectives of the practitioner as well as the patient.

For all patient data collection forms completed in the practitioner's office after the enrollment visit, the dentist's staff will be responsible for mailing the study data collection forms to the RAS.

8 ASSESSMENT OF SAFETY

8.1 Specification of Safety Parameters

Safety monitoring for this study will focus on unanticipated problems involving risks to participants, including unanticipated problems that meet the definition of a serious adverse event.

8.1.1 Unanticipated Problems

The Office for Human Research Protections (OHRP) considers unanticipated problems involving risks to patients or others to include, in general, any incident, experience, or outcome that meets **all** of the following criteria:

- Unexpected in terms of nature, severity, or frequency given (a) the research procedures that are described in the protocol-related documents, such as the IRB-approved research protocol and informed consent document; and (b) the characteristics of the patient population being studied;
- Related or possibly related to participation in the research (possibly related means there is a reasonable possibility that the incident, experience, or outcome may have been caused by the procedures involved in the research); and
- Suggests that the research places patients or others at a greater risk of harm (including physical, psychological, economic, or social harm) than was previously known or recognized.

8.1.2 Serious Adverse Events

A serious adverse event (SAE) is one that meets one or more of the following criteria:

- Results in death.
- Is life-threatening (places the subject at immediate risk of death from the event as it occurred).
- Results in inpatient hospitalization or prolongation of existing hospitalization.
- Results in a persistent or significant disability or incapacity.
- Results in a congenital anomaly or birth defect.

An important medical event that may not result in death, be life threatening, or require hospitalization may be considered an SAE when, based upon appropriate medical judgment, the event may jeopardize the patient and may require medical or surgical intervention to prevent one of the outcomes listed in this definition.

8.2 Reporting Procedures

Incidents or events that meet the OHRP criteria for unanticipated problems require the creation and completion of an unanticipated problem report form. OHRP recommends that investigators include the following information when reporting an AE, or any other incident, experience, or outcome as an unanticipated problem to the IRB:

- Appropriate identifying information for the research protocol, such as the title, investigator's name, and the IRB project number;
- A detailed description of the AE, incident, experience, or outcome;
- An explanation of the basis for determining that the AE, incident, experience, or outcome represents an unanticipated problem;
- A description of any changes to the protocol or other corrective actions that have been taken or are proposed in response to the unanticipated problem.

To satisfy the requirement for prompt reporting, unanticipated problems will be reported using the following timeline:

- Unanticipated problems that are SAEs will be reported to the IRB and to NIDCR within 1 week of the investigator becoming aware of the event.
- Any other unanticipated problem will be reported to the IRB and to NIDCR within 2 weeks of the investigator becoming aware of the problem.
- All unanticipated problems should be reported to appropriate institutional officials (as required by an institution's written reporting procedures), the supporting agency head (or designee), and OHRP within one month of the IRB's receipt of the report of the problem from the investigator.

All unanticipated problems will be reported to NIDCR's centralized reporting system via Rho Product Safety:

- Product Safety Fax Line (US): [name]
- Product Safety Fax Line (International): [contact]
- Product Safety Email: [contact]

General questions about SAE reporting can be directed to the Rho Product Safety Help Line (available 8:00AM – 5:00PM Eastern Time):

- US: [name]
- International: [contact]

9 STUDY OVERSIGHT

The GPI and SPI will be responsible for study oversight, including monitoring safety, ensuring that the study is conducted according to the protocol and ensuring data integrity. In addition to the SPI's responsibility for oversight, study oversight will be under the direction of the NIDCR Medical Monitor. The SPI will submit reports to NIDCR Medical Monitor for review at six months after study initiation until enrollment targets have been met, and then annually thereafter. Medical Monitor reports will include data regarding enrollment and retention, unanticipated problems and protocol deviations, primary outcome measures, quality management findings and other relevant parameters. If necessary, additional steps may be taken to ensure data integrity and protocol compliance.

10 CLINICAL SITE MONITORING

Clinical site monitoring is conducted to ensure that the rights of human subjects are protected, that the study is implemented in accordance with the protocol and/or other operating procedures, and that the quality and integrity of study data and data collection methods are maintained. The network RAS will be responsible for clinical site monitoring for this study. RCs at each RAS will provide study training to practitioner sites and will perform quality management and clinical site monitoring activities, to evaluate study processes and documentation based on NIDCR standards and principles of good clinical practice (GCP).

Quality management procedures are detailed in the protocol, Section 13, as well as the study-specific Manual of Procedures (MOP). This study will follow the general guidelines for conducting monitoring for the network's observational clinical studies documented in Chapter 6 of the National Dental PBRN Manual of General Operations. Documentation of monitoring activities and findings will be provided to the practitioner, GPI, SPI, NIDCR Office of Clinical Trials Operations and Management, and the NIDCR Program Official. The NIDCR reserves the right to conduct independent audits as necessary.

11 STATISTICAL CONSIDERATIONS

11.1 Study Hypotheses

The primary objective is to estimate the proportion of patients 1) treated successfully (determined at end of active treatment), and 2) whose treatment is stable (determined at one year post active treatment).

11.2 Sample Size Considerations

Previous studies have reported success rates around 80% for treatment of AOB, and among those successfully treated, from 65% to 100% have been reported to be stable. These success and stability rates are likely overestimated due to reporting bias. We want to estimate both success and stabilization rates with 10% precision. Power is weakest when success and stabilization rates are lower (need larger sample size [patients], see table below).

Total number of patients needed to estimate proportions with 10% precision	
%succeed/stabilize	3/dentist
50%	422
60%	406
70%	355
80%	271
90%	153
Assumes interclass correlation coefficient (ICC) of 5%	

Assuming a 70% success rate, a 50% stabilization rate, an average of 3 patients per practitioners and an ICC of 5%, 600 patients are needed. To allow for a 10% attrition for success (end of treatment) and 20% attrition for stabilization (one year post treatment), this study would need to enroll 840 patients. This means we need to recruit about 210 orthodontists, who each need to recruit about 4 patients each.

11.3 Final Analysis Plan

Analysis plan for Primary Objectives:

Primary objective #1 is to estimate the proportion of patients who are successfully treated. As described in section 3.2 (outcome measures), successful treatment is defined as occurring when patients have positive overlap at the end of treatment; this will be calculated with a 95% confidence interval.

Though not an explicit hypothesis, we expect those that are “successfully” closed will have had a smaller distance between the maxillary and mandibular incisor tips prior to treatment, i.e., at enrollment, than those not successfully closed. We will calculate the mean distance improved separately for those successfully treated and those not. It may be that those not successfully treated had more improvement than those who were successfully treated (if the former had a greater distance that needed to be corrected) and we want to capture this. Thus, as an additional but secondary measure of improvement, we will also calculate mean and median distance improved as descriptive measures.

Primary objective #2 is to estimate, among patients who are successfully treated, the proportion of patients whose treatment is stable. As described in section 3.2 (outcome measures), stability will be assessed one year after end of active treatment. The primary measure (strictest, most conservative classification) will be among patients who are determined to have been successfully treated at end of active treatment (having closed their AOB), what proportion of these have positive overlap at the one-year follow up time. This proportion will be estimated with a 95% confidence interval. Additional assessments of stability will include the proportion of all who had improvement in overbite (positive increases) during retention, no change in overbite during retention, and worsening of overbite (negative increases) during retention. We will calculate these mean and median changes as descriptive measures.

11.4 Secondary Analyses

11.4.1 Sample Size Considerations

For secondary objectives, we wish to detect differences of 20% in success and stabilization rates between subgroups, e.g., differences between patients for whom extraction was recommended and those for whom it was not. In general, we will need 110 patients for each group that is being compared (assuming 80% power, 5% significance level, and an ICC of 5%). For example, for the assessment of success between extraction and non-extraction cases, we need 110 patients treated with each technique. For the comparison of the four treatment modalities, we need 110 patients treated with each of the 4 techniques, or 440 patients total. If we recruit 840 patients at baseline, we should have adequate power for most secondary objectives, even allowing for attrition.

11.4.2 Proposed Secondary Analyses

Analysis plan for Secondary Objectives:

Secondary objective #1a will examine how dentofacial, as well as patient and practitioner characteristics influence treatment recommendations suggested by the orthodontists. The association of each of the dentofacial, patient and practitioner characteristics specified below with different treatment recommendations will be ascertained using a chi-square test for categorical variables and either t-test or Wilcoxon rank-sum test (nonparametric equivalent). Dentofacial characteristics: profile, molar classification, maxillary crowding, mandibular crowding, posterior cross-bite, facial pattern. Patient characteristics: age, sex, race/ethnicity, insurance, education, treatment goals. Practitioner characteristics: age, sex, race/ethnicity, year received orthodontic training. For each domain of the three domains, namely, dentofacial, patient and practitioner characteristics, characteristics with $p < 0.2$ will be entered in the model, retained if $p < 0.1$. Final Generalized Estimating Equations (GEE) regression model (adjust for clustering within practice) will start with those $p < 0.1$ for each domain, and retained if $p < 0.05$ for final analysis ascertaining how dentofacial, as well as patient and practitioner characteristics influence treatment recommendations (extraction, then surgical component, fixed appliances, removable aligners, TADs).

Secondary objective #1b will examine how dentofacial, as well as patient, practitioner, characteristics influence whether or not treatment recommendations suggested by the orthodontists are accepted by the patients. Method described above will be repeated for acceptance of recommendations. Separate analyses, i.e., stratum specific, will be performed for recommendations involving extraction and those not. Of interest (though not a primary objective or specific hypothesis to be tested) within this secondary objective is exploring what factors influence whether or not patients accept treatment recommendations involving an extraction or surgical component.

Secondary objective #2a will identify how treatment modalities, as well as dentofacial, patient and practitioner characteristics, are associated with treatment success. Success is defined above, first as positive overbite, then as amount of millimetric improvement, even if AOB is not completely closed as described in analysis for primary objective #1 above. Separate analyses, i.e., stratum specific, will be performed for treatment involving extraction and those not. The association of treatment modalities used will be assessed with whether or not treatment was successful using chi-square. The dentofacial, patient and practitioner characteristics described above, and the process to ascertain their influence on treatment recommendations, will be used to determine their association with treatment success. The process, being domain specific, will model criteria entry if $p < 0.2$; retain at $p < 0.1$. Final model, all domains combined, entry if $p < 0.1$; retained if $p < 0.05$. For this secondary objective (2a), treatment modalities will be included, first as a domain in the same manner that dentofacial, patient, and practitioner characteristics are. Then, stratum specific analyses will be performed separately according to whether or not there was an extraction.

Secondary objective #2b will identify how treatment modalities, as well as dentofacial, patient and practitioner characteristics, are associated with patient satisfaction. The above process will be repeated except the “outcome” will be patient satisfaction instead of treatment success. Separate models will be developed for overall or general

satisfaction, and for satisfaction with esthetics and with function. For this objective, whether or not treatment was successful, will be analyzed as an independent variable. A high association is expected, namely, more patients will be satisfied when treatment is successful than when not; however, it will not be a 100% (perfect) association. Some patients who are treated successfully will not be satisfied, and in contrast, some patients who are not treated successfully will be satisfied. Quantification of these proportions is of interest, as well as identifying characteristics (treatment modalities, dentofacial, patient and practitioner) that are associated with satisfaction (or dissatisfaction).

Secondary objective #3a will examine how retainer regimens, as well as treatment modalities, dentofacial, patient and practitioner characteristics are associated with treatment stability. Stability is defined above, namely, at one year after end of active treatment there is positive overbite. First, the association of retainer regimens, namely, type of retainer (Hawley, Essix, bonded) and frequency of use prescribed (full or part-time) with treatment stability will be assessed with chi-square test. The treatment modalities (extraction, then surgery, fixed appliances, removable aligners, or TADs), dentofacial, patient and practitioner characteristics described above, will be used to ascertain their association with treatment stability. The process, being domain specific, will model criteria entry if $p < 0.2$; retain at $p < 0.1$. Final model, all domains combined, entry if $p < 0.1$; retained if $p < 0.05$. For this secondary objective (3a), retainer regimens will be included, first as a domain in the same manner that treatment modalities, dentofacial, patient, and practitioner characteristics are. Then, stratum specific analyses will be performed separately according to whether or not treatment included extraction and whether or not treatment was successful (AOB closed at end of active treatment).

Secondary objective #3b will examine how retainer regimens, as well as treatment modalities, dentofacial, patient and practitioner characteristics are associated with patient satisfaction, assessed one year after end of active treatment. The above process will be repeated except the “outcome” will be patient satisfaction at one year after end of active treatment instead of treatment stability. Separate models will be developed for overall or general satisfaction, and for satisfaction with esthetics and with function; all ascertained at one year after end of active treatment. For this objective, whether or not treatment was stable will be analyzed as an independent variable. A high association is expected, namely, more patients will be satisfied when treatment is successful than when not; however, it will not be a 100% (perfect) association. Some patients who are treated successfully will not be satisfied, and in contrast, some patients who are not treated successfully will be satisfied. Quantification of these proportions is of interest, as well as identifying characteristics (treatment modalities, dentofacial, patient and practitioner) that are associated with satisfaction (or dissatisfaction).

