4 STUDY DESIGN

- This will be a prospective, observational 3.5-year cohort study of patients who are undergoing different types of orthodontic AOB treatment followed by retainers.
- The study population will consist of adult patients who are in active treatment for AOB, and expect to have treatment completed within 24 months of enrollment into the study. Approximately 210 orthodontists or dentists who routinely perform orthodontic treatment (approximately 35 in each of the six National Dental PBRN regions) will participate. Actual enrollment will be based on interest and enrollment into the Network, and likely will vary per region. Each practitioner will be requested to enroll approximately 3 - 8 adult patients in active AOB treatment over an approximate 11 -months enrollment period, with an enrollment goal of approximately 840 adult patients across the National Network. No practitioner will contribute more than 15 patients.
- Retrospective data will be collected to explore patient, practitioner, and dentofacial characteristics that influence the treatment recommendations and the accepted treatment plans for patients with AOB.
- The prospective cohort design will allow the investigation of how patient, practitioner, and dentofacial characteristics affect the success of treatment. The treatment provided to the patients will not be influenced at all by participation in the study.
- In addition, this study will allow the assessment of how treatment modalities, retainer regimens, and patient characteristics are associated with treatment stability and patient satisfaction one year after treatment.
- At each routinely scheduled retainer check visit, the patient will be asked to report on their retainer usage, and the practitioner will also be asked to judge retainer use.
- Patients will be asked again about satisfaction with their retainer regimen, as well as esthetics and function, at one year after treatment.
- Patients will participate in the study for approximately 3 years, on average, the duration of the treatment and follow-up phases. Practitioners' participation in the study will be approximately 3.5 years.

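### The bivariate tests in Protocol 11.4.2 ignore the within-practitioner clustering that the sample size allows for; the effect is modest and falls mainly on practitioner characteristics

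*Protocol*

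**What the plan says.** **Sizing.** The table in Protocol 11.2 carries the note "Assumes interclass correlation coefficient (ICC) of 5" per cent. The text below it works from "an average of 3 patients per practitioners and an ICC of 5%, 600 patients are needed", then enrols 840 patients through about 210 orthodontists "who each need to recruit about 4 patients each". Section 11.4.1 uses the same ICC to reach 110 patients per compared group. Section 4 asks for roughly 3 to 8 patients each and sets a ceiling: "No practitioner will contribute more than 15 patients".

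**Secondary analysis.** For objective 1a, section 11.4.2 says that the associations "will be ascertained using a chi-square test for categorical variables and either t-test or Wilcoxon rank-sum test". Characteristics with p<0.2 enter a model for their domain and stay at p<0.1. The survivors go into a final GEE model that adjusts for clustering within practice, with retention at p<0.05. For objective 2a: "The association of treatment modalities used will be assessed with whether or not treatment was successful using chi-square". For objective 3a, retainer type and prescribed frequency of use "with treatment stability will be assessed with chi-square test". Objective 2a refers back to the 1a process. Objective 3a repeats the thresholds and mentions a final model without naming GEE, and 3b repeats 3a.

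**Primary analysis.** For the success proportion, section 11.3 says only that "this will be calculated with a 95% confidence interval". The stability proportion is worded similarly. Neither sentence gives an interval method.

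**The concern.** The plan accepts at the sizing stage that patients of one practitioner resemble each other, then names tests whose reference distributions assume they do not. Three consequences follow.

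- The p<0.2 screen decides which variables can reach the GEE, and it runs without the adjustment. The domain models are not described as adjusted either.
- The chi-squares for modality against success and retainer regimen against stability are stated as assessments in their own right. Section 11.4.1 uses comparisons of this kind to justify 110 per group with an ICC of 5%, yet the test named for them drops the ICC.
- Practitioner age, sex, race/ethnicity and training year take one value per practitioner. About 210 independent values are analysed as if there were about 840.

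At stake is an excess of false positives, chiefly for practitioner factors. In objective 1a the outcome is the practitioner's own recommendation, so clustering above 5% is plausible, but the documents give no figure for it.

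**Working it through.** **Inputs from the protocol.** ICC 0.05 (11.2, 11.4.1); 3 patients per practitioner for sizing, about 4 at enrolment, about 210 practitioners (11.2); maximum 15 (section 4); assumed success 70% and stability 50%, attrition 10% and 20% (11.2).

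**Assumptions not in the protocol.** A coefficient of variation (CV) of cluster size of 0.68 to 0.73, and an alternative ICC of 0.10.

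**1. The plan's own figures.** n = 1.96² × p(1−p) / d² × [1 + (m−1) × ICC]. With m = 3 the design effect is 1 + 2 × 0.05 = 1.10. With d = 0.05 (10 points total width):

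| Rate | Without clustering | × 1.10 | Protocol |
|---|---|---|---|
| 50% | 384.1 | 422.6 | 422 |
| 60% | 368.8 | 405.7 | 406 |
| 70% | 322.7 | 355.0 | 355 |
| 80% | 245.9 | 270.4 | 271 |
| 90% | 138.3 | 152.1 | 153 |

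The table therefore contains the cluster inflation. Base rates behind the 110 per group are not stated; for 40% against 60%, 97 per group × 1.10 = 106.7 and × 1.15 = 111.5, so 110 is also consistent with an inflated figure.

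**2. True size for a practitioner-level factor.** DEFF = 1 + [(1 + CV²)m − 1] × ICC, and true size = 2 × [1 − Φ(z/√DEFF)], with z = 1.960 for a 5% test and 1.282 for the 20% screen.

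| ICC | m | CV | DEFF | Nominal 5% | Nominal 20% |
|---|---|---|---|---|---|
| 0.05 | 3 | 0 | 1.10 | 6.2% | 22.2% |
| 0.05 | 4 | 0 | 1.15 | 6.8% | 23.2% |
| 0.05 | 4 | 0.68 | 1.24 | 7.9% | 25.0% |
| 0.05 | 4 | 0.73 | 1.26 | 8.0% | 25.3% |
| 0.10 | 4 | 0 | 1.30 | 8.6% | 26.1% |
| 0.10 | 4 | 0.68 | 1.49 | 10.8% | 29.3% |

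Beta-binomial simulations agree. With equal clusters at ICC 0.05, the 5% test rejected 6.2% (m = 3) and 6.6% (m = 4) of the time, and the 20% screen 22.1% and 23.2%. With mean 4, cap 15 and CV 0.68, the 5% test rejected 7.9% at ICC 0.05 and 10.7% at ICC 0.10.

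**3. Patient-level covariates.** Here the size depends on how strongly the covariate itself clusters, which the documents do not give. With outcome ICC 0.05 and covariate ICC of about 0, 0.2 and 0.5, simulated size at nominal 5% was 5.0 to 5.6% over m = 3 and m = 4. If modality and retainer regimen cluster no more than this, the two stand-alone chi-squares are close to nominal at the protocol's ICC.

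**4. Primary intervals, if computed as simple binomial.** Coverage = 2Φ(1.96/√DEFF) − 1.

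- Success: 840 × 0.9 = 756 patients, or 756/210 = 3.6 per practitioner. DEFF = 1.13 and coverage 93.5%. At m = 4 it is 93.2% with equal clusters and about 92% with CV 0.68 to 0.73. Half-width at 70% is 3.27 points unadjusted and 3.50 with DEFF 1.15.
- Stability: 840 × 0.9 × 0.8 × 0.7 = 423 patients, or about 2 per practitioner. DEFF = 1.05 and coverage is about 94%.

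**The case against.** **Final inference is already clustered.** The 1a tests are a first-stage screen. The stated final analysis is a GEE, which 2a inherits by reference. Modalities (2a) and retainer regimens (3a) also enter as domains and pass to a final model. A slightly liberal screen mainly admits extra candidates, which are then tested at p<0.05. This stands for 1a and 2a, so a reader should not infer that the secondary objectives go without cluster adjustment. It does not remove the stand-alone chi-squares, the domain models with no stated adjustment, or the 3a and 3b final models for which GEE is not named.

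**Primary intervals.** A reader might infer that the primary confidence intervals are too narrow. The documents do not support that: section 11.3 gives no method, the sizing allows for clustering, and interval methods are commonly left to a statistical analysis plan, which is not shown. Nor does it follow from chi-square, t and Wilcoxon tests, which yield p-values. The coverage figures above are conditional on a simple binomial interval.

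**Larger error rates.** Rates near 17 to 22% can be produced for practitioner factors, but only with an ICC of 0.2 to 0.3 and unequal clusters. The protocol gives no such ICC, so these figures should not describe the plan.

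**Cluster-size variation.** A CV near 0.7 is also an assumption. Section 4 requests 3 to 8 patients and 15 is only a ceiling; a uniform spread over 3 to 8 has a CV of about 0.31. With m = 4 and CV 0.35, DEFF is 1.17 and size about 7%. This is fair, and is why a range is given. Any inequality in cluster size still pushes above the equal-cluster values.

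**Conclusion.** The point holds for the named bivariate tests. They assume independence in a study sized for clustering, and the only stated adjustment comes later, in the final GEE.

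The consequence is modest and uneven. For practitioner characteristics at the protocol's ICC, a 5% test runs at about 6 to 7% with equal clusters of 3 to 4 and about 8% with CV near 0.7; the 0.20 screen passes about 22 to 25% of null factors. If recommendations cluster at an assumed ICC of 0.10, the 5% test runs at about 9 to 11% with 4 patients per practitioner. Patient-level covariates with little clustering are essentially unaffected.

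For the primary proportions there is no stated error, only a method to be made explicit: a simple binomial interval, if used, would cover about 92 to 94%.

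The clustering unit also differs. Section 11.2 counts patients per practitioner, while 11.4.2 adjusts within practice. The two are not the same where several practitioners share a practice.

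**What to change.** In 11.4.2:

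- Replace the chi-square, t and Wilcoxon tests by single-predictor GEE models with robust standard errors, clustered on practitioner. Rao-Scott chi-square will serve for descriptive tables. This includes the modality test in 2a and the retainer-regimen test in 3a.
- State that the domain models, and the final models for 3a and 3b, are also fitted by GEE.
- Use one clustering unit throughout; practitioner matches the sizing.

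In 11.3, state that both primary 95% intervals use a cluster-robust variance, for example from an intercept-only GEE with exchangeable correlation, in line with the sizing in 11.2.

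The cost is revised wording and a few lines of code, with no extra patients or data. Some p-values will be larger and the intervals slightly wider than simple binomial ones; the sample size already allows for this.
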